**Endpoints:**

- The primary Efficacy Endpoint:  
The average AF burden.
- The secondary Efficacy Endpoint(s):
  - 1) Time-dependent reduction of AF burden
  - 2) Ventricular rate during AF
  - 3) average SKNA
  - 4) Quality of life

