The patients will be admitted to the hospital and undergo surgical procedure for implantation of externalized subcutaneous neurostimulation lead for ScNS. The patients will be monitored while the stimulation protocol is started. The stimulation in the experimental group will continue for two weeks while all the patients are continuously monitored by the Mobile Cardiac Telemetry system. The lead will be removed at the 2 weeks visit. 7-day mobile cardiac telemetry will be performed at the 2 week and 3-month visits. The study ends after the final week of outpatient cardiac monitoring is performed. The control group will have an option to cross over to the experimental group 3 weeks post-procedure. They will undergo a second procedure and receive stimulation for two weeks. The lead will be removed after stimulation is complete. 7-day mobile cardiac telemetry will be performed for three weeks and at the post 3-month visit.

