## 4 STUDY DESIGN

### 4.1 OVERALL DESIGN

- *A statement of the hypothesis.*
  - To test the hypothesis that ScNS can be used to reduce the AF burden in patients with paroxysmal AF
- *Phase of the trial.*
  - Not applicable.
- *A description of the type/design of trial to be conducted (e.g., randomized, placebo-controlled, double-blinded, parallel design, open-label, dose escalation, dose-ranging, adaptive, cluster randomized, group sequential, multi-regional, superiority or non-inferiority design).*
  - This is a prospective randomized IDE study. The patients are randomized into Experimental and Control groups. There is an option for the Control group to crossover into the Experimental group after completion of obtaining the primary endpoint.
- *A description of methods to be used to minimize bias.*
  - The investigators are responsible for programming the device and cannot be blinded to the study. However, we will not tell the patients whether they are randomized into the experimental or the control group until the primary endpoint is complete. Technicians and physicians responsible for echocardiogram and ECG monitoring will be blinded.
- *The number of study groups/arms and study intervention duration.*
  - We will randomize the patients into:
    - Group A: Experimental group will undergo 3.5 mA ScNA for two weeks.
    - Group B: Sham control group will receive 0 mA stimulation for two weeks.

- *Indicate if single site or multi-site.*
  - This is a single site study.
- *Name of study intervention(s).*
  - Subcutaneous nerve stimulation (ScNS).

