### 6.3 MEASURES TO MINIMIZE BIAS: RANDOMIZATION AND BLINDING

The patient will be consented to undergo surgery. After the device implantation, the patients will be randomized to experimental and control groups using Redcap. We will attempt to blind the patients, although the tingling or pain associated with the stimulation may make blinding difficult. All data analyses performed by the co-investigators and the rhythm analyses performed by the Mobile Cardiac Telemetry system technicians will be blinded. The experimental group will receive stimulation at 3.5 mA output, while the control group will receive no stimulation. Data will be obtained during this time to determine atrial arrhythmia frequencies in both groups. The device will then be removed at the end of the second week. After the third week, we will give the option to the control group to crossover to the experimental group. This group of patients will undergo a second procedure to receive stimulation at 3.5 mA and we will follow up for another 3 weeks and 3 months post second procedure.

We will tell the patients that they will be randomized into experimental group or control group during surgery. We will attempt to blind the patients, although the tingling or pain associated with the stimulation may make blinding difficult. We will explain to all patients they may or may not feel tingling and/or pain during the 2-week stimulation time but will not tell them which group they are assigned to. All data analyses performed by the co-investigators and the rhythm analyses performed by the 7-day non-invasive monitoring system technicians will be blinded. After 3 weeks post-procedure, we will unblind the control group to give them the option of crossing over to the experimental group to receive the treatment. If they agree, these group of patients will forego the 3-month follow-up visit and will proceed with a second procedure along with follow up visits post-second procedure. Data will be obtained during this time to determine AF burden in all groups.

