### **Analysis of SKNA and QOL**

Subcutaneous nerve stimulation achieves its effects through neuromodulation, resulting in reduced sympathetic nerve activity. A non-invasive method to measure sympathetic nerve activity is through the skin sympathetic nerve activity (SKNA) recording. We will record SKNA using two different equipment. The first is ME6000 which makes high fidelity SKNA recordings with 10,000 Hz sampling rate. However, ME6000 is not sufficiently portable for ambulatory recordings. Therefore, we added Bittium Faros recorder for ambulatory recording at 1,000 Hz sampling rate.

The quality of life (QOL) is measured using the standard questionnaire to assess the overall effects of treatment on the study subjects.

SKNA recorded with ME6000 at rest and during 6-minute walk will be summarized at each time point using mean and standard deviation.

SKNA recorded with Bittium Faros when patients were ambulatory will be summarized at each time point using mean and standard deviation.

Quality of life (AFEQT-AF, EQ-5Q-5L) will be summarized by item and by overall score at the following time points, baseline, 3 week and 3-month visits using mean and standard deviation.

Change in the average values of SKNA (aSKNA) recording at rest on the procedure day from the baseline will be compared between the randomization groups using the Wilcoxon Rank Sum test. Values of aSKNA recording in ambulatory subjects and during 6-minute walk at baseline, 1 week, 2-week, 3 week and 3-month visits will be compared between randomization groups using linear mixed models, with Group, Week and Group-Week interaction as fixed effects, and a random intercept per subject. Week will be coded first as a categorical variable. If aSKNA appear to be linear in time, we may model Week as a continuous fixed effect. Missing at random will be assumed in the above stated linear mixed models. Additionally, the strategy of last-value-carried-forward (LVCF) will be employed to fill in missing data values as an alternative to the missing-at-random assumption and the linear mixed models will be re-

run. The LVCF analysis serves as a sensitivity analysis. Similar analyses will be performed for SKNA during 6-minute walk.

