		
2. Optional Crossover study after Week 3
 
3. Addition of Secondary Endpoint regarding the optional crossover study
	
recordings were done within 6 months prior to enrollment and there are no changes in antiarrhythmic medications after the recording, then the AF burden recorded by the ePatch will be used as baseline AF burden. This change will eliminate the need of repeating the ePatch recording for eligibility determination and thus improve recruitment.
 
Based on our DSMB recommendations from 9/22/22, we are doing a crossover after week 3 to improve recruitment because all participants are guaranteed an opportunity to receive subcutaneous stimulation. In our original protocol, after the first 3 weeks, additional data collection will be performed with Apple Watch and with a final one-week ePatch monitoring. However, since the latter data are used for secondary exploratory analysis only, we do not need those data to determine the primary endpoint of the study.

10	12-30-2022	
1. Removed Catecholamines and BNP for Week 3 Visit. The labs required for a second procedure are only to ensure that the subject is ready for surgery.
	Per PI, we do not need catecholamines nor BNP to undergo the second surgery.
11	01-18-2023	
1. We are removing the verbiage that states postdocs will be blinded during SKNA data analysis.
	
In the first 4 patients who underwent stimulation, large stimulation artifacts were noted in the recording. Therefore, the postdoc can immediately recognize who's been stimulated and who's not just by looking at the data. It is not possible to blind the postdoc during data analyses

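### The stimulation-artifact reason for dropping postdoc blinding of SKNA analysis covers only recordings made before lead removal, yet the plan provides no blinded SKNA reading for the later ones

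*Combined protocol and SAP*

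**What the plan says.** Average SKNA is the third secondary efficacy endpoint (synopsis, section 3 and section 9.1).

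In section 10.4 the version 11 entry states: "We are removing the verbiage that states postdocs will be blinded during SKNA data analysis". The reason follows: "In the first 4 patients who underwent stimulation, large stimulation artifacts were noted in the recording", so that anyone looking at the data can tell who was stimulated, and "It is not possible to blind the postdoc during data analyses". The entry does not separate recordings made during stimulation from those made after it.

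Two statements about blinded readers remain in the current text. Section 4.1 says: "Technicians and physicians responsible for echocardiogram and ECG monitoring will be blinded". Section 6.3 says, and then nearly repeats: "All data analyses performed by the co-investigators and the rhythm analyses performed by the Mobile Cardiac Telemetry system technicians will be blinded". Neither mentions SKNA.

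On timing, section 1.2 says: "The lead will be removed at the 2 weeks visit". The schedule in section 1.3 places resting SKNA at baseline, the procedure day, weeks 1, 2 and 3, and month 3, and walk SKNA at the same visits except the procedure day. Section 9.4.3 plans one between-arm test at rest (procedure day minus baseline, Wilcoxon). Ambulatory SKNA and SKNA "during 6-minute walk at baseline, 1 week, 2-week, 3 week and 3-month visits will be compared between randomization groups using linear mixed models".

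**The concern.** Artifact identifies the arm only while current flows. Inside the two-week window it marks Group A, and its absence marks Group B. Once the lead is out, neither arm carries it. The reason given is therefore narrower than the change it supports, and the current text does not restore protection for the later recordings.

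Section 6.3 is also unclear. If its sentence on co-investigator analyses covers SKNA, the version 11 entry shows that the promise cannot be kept for stimulation-on files. If it does not, SKNA has no stated analyst blinding.

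At stake is the reading of SKNA at week 3 and later. An analyst who knows the arm and has any discretion over noise or segment selection could create or enlarge a group difference. With no masking and no fixed processing rule in 9.4.3, a reader of the results could not exclude this.

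**Working it through.** The plan states no figure for the share of SKNA recordings made with the stimulator off, so there is none to reproduce. The count below is per patient.

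**Inputs.** Visits come from the schedule in 1.3 and from 9.4.3. Faros wear is assumed to follow the telemetry time points in 8.1 (eligibility, procedure, week 1, week 2, month 3), because 1.2 says the two devices are applied at similar times. Stimulation is assumed continuous from the procedure to lead removal at week 2; no pause for recording is described. Section 6.3 places randomisation after the implant, so baseline recordings precede allocation.

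**Count after randomisation.** Base case: the procedure-day and week-2 clinic recordings count as on.

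| Recording | Scheduled | Outside the stimulation window | Control who crosses over (no month 3) |
|---|---|---|---|
| Rest | procedure, weeks 1, 2, 3, month 3 = 5 | week 3, month 3 = 2 (40%) | 1 of 4 |
| Walk | weeks 1, 2, 3, month 3 = 4 | week 3, month 3 = 2 (50%) | 1 of 3 |
| Faros (start of wear) | procedure, weeks 1, 2, month 3 = 4 | from week 2, month 3 = 2 (50%) | 1 of 3 |
| All | 5 + 4 + 4 = 13 | 6 (46%) | 3 of 10 (30%) |

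Adding one pre-randomisation recording to each row gives 3/6, 3/5 and 3/5, or 9/16 (56%).

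**Unstated order of events.** For clinic recordings after randomisation the base case is 4/9 (44%). It becomes 5/9 (56%) if the procedure-day recording precedes switch-on, or 6/9 (67%) if the week-2 recordings follow lead removal.

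**Where the off recordings enter a test.** The resting test uses procedure day minus baseline; resting values at week 3 and month 3 are only summarised. The walk and ambulatory values enter mixed models with group, week and their interaction, so the between-arm contrasts at issue lie there.

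**Illustration only.** Assume, without support in the documents, that unblinded handling shifts Group A by 0.25 to 0.5 SD when there is no true effect. For a two-sided 0.05 two-sample t test with n per arm, the non-centrality is d × √(n/2) on 2n − 2 degrees of freedom.

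- n = 10 (15 × 0.70 = 10.5, rounded down): non-centrality 0.559 and 1.118; rejection 8.3% and 18.5%.
- n = 15: non-centrality 0.685 and 1.369; rejection 10.1% and 26.2%.

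This shows sensitivity to an assumed shift. It is not an estimate for this trial, and the planned SKNA analyses are a rank-sum test and mixed models.

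**The case against.** The strongest reply is that the plan loses little. The log entry concerns postdocs only, 6.3 keeps co-investigator analyses blinded, and SKNA is a mechanistic secondary endpoint reported with nominal p-values. Nothing in the plan describes manual segment selection; 9.4.3 speaks of average values. A reader who has seen a patient's week-1 file already knows the arm, and section 10.1.3 gives each participant one study number, so removing the blinding statement may simply have been candid.

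Much of this stands, and it limits what can be claimed.

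- A reader might infer that version 11 ended blinding of all SKNA analysis, or that SKNA is read open-label. The documents do not say who reads SKNA. They support only that no blinded SKNA reader is named and that the scope of the 6.3 sentence is unclear.
- A reader might infer that half of the recordings are needlessly exposed. The share passes one half only when baseline, which precedes allocation, is counted, or when an unstated order of events is resolved in that direction.
- A reader might take month 3 as the cleanest contrast. By then controls have been unblinded and those who cross over have left that comparison, so it is selected by patient choice. Week 3 does not have this defect.

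The reply does not remove the point. Linkage through the study number is what per-file coding breaks, and silence about processing rules does not protect against discretion in applying them.

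**Conclusion.** The concern holds in a limited form. The stated reason justifies unblinded reading of stimulation-on SKNA files and of nothing else. For recordings outside the window (2 of 5 at rest and 2 of 4 during the walk after randomisation, with week 3 only for crossover controls, plus the Faros recordings started after lead removal) analyst blinding remains feasible if files are recoded. The plan does not provide it. The contrasts mainly affected are the week-3 walk and the ambulatory comparisons.

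The result is an avoidable risk of bias of unknown size and direction in secondary endpoint 3. It does not show that bias has occurred. It does not extend to the primary AF-burden endpoint, whose rhythm analyses are stated to be blinded. Blinding is not recoverable for stimulation-on files, which probably include the procedure-day recording in the resting test. The conclusion rests on stimulation being continuous up to lead removal and on Faros wear following the telemetry schedule.

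**What to change.** In 6.3 and 9.4.3, state the following.

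- SKNA files recorded with the stimulator off (baseline, week 3, month 3, Faros recordings after lead removal, and week 2 if recorded after removal) go to the analyst under a separate random code for each file, with patient ID, visit and date removed. They are processed with the same fixed settings, and linkage is restored only when processing is complete. Baseline is included because its files may be read after allocation is known.
- SKNA files recorded during stimulation are analysed unblinded and reported as such.
- The sentence in 6.3 on co-investigator analyses is limited accordingly, at both places where it appears.

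Record for each procedure-day and week-2 SKNA file whether stimulation was on, so that it can be assigned to the right group.

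The cost is relabelling by a coordinator, files that stay unlinked until processing ends, and reprocessing under code of any stimulator-off files already read. No new visit, procedure, patient or reader is needed.
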